3. STUDY DESIGN

Study Design

A mixed-methods cross-over observational study will be conducted to explore the safety, performance, and user perceptions of utilising RxConnect to support prescribing, in comparison to current practice.

Direct observation of participants will be conducted using multi-angle audio-visual recording, this will be set up behind the computer workstation, to capture the computer display and from above to capture the workstation. The cameras will not be angled to take footage of the participant face. A member of the research team will also be present through the study session.

Prescribing scenarios will be presented on laminated paper along with any relevant patient information, e.g. patient gender, age, weight, diagnosis, relevant medical history, relevant laboratory results.

Intervention arm: Prescribing with RxConnect via a prototype user interface

Participants will be asked to complete a number of practice prescribing tasks whilst *thinking aloud* to describe their thought process and actions. To undertake the prescribing tasks, participants will be asked to use the prototype user interface emulating an electronic prescribing front end, which presents RxConnect medication guidance to the clinical end user (the participant).

Once familiarised with the software workflow, the test prescribing tasks will be given to the participant. For these tasks the participants will be asked to perform the task without the need to think aloud. If the participant wishes to continue to think aloud so long as it doesn't distract

them from completing the task. The medication order the participants have generated using RxConnect support via the user interface will then auto populate a medication order form.

Control arm: Prescribing on Cerner with existing resources

Participants will be asked to perform similarly simple and then complex tasks using their usual practice methods when prescribing. Access will be provided to the prescribers usual electronic prescribing platform, including links to the British National Formulary, Medicines complete, local antimicrobial stewardship application, local intranet, and a generic online search engine. A hard copy of the BNF and BNFc will also be readily available.

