As with the intervention arm, if the participant wishes to continue to think aloud so long as it doesn't distract them from completing the task. Participants will be asked to enter their medication order for the patient within a 'test ward' on the Cerner Millennium Powerchart system.

Order of control vs intervention arm-

Each participant will be randomly assigned to begin with either the control arm or the intervention arm (Group 1 and Group 2, see Table 1). With an equal number of participants being in each group. A random team generator (https://www.randomlists.com/team-generator) will be used for randomisation (see Figure 1) and participants will be assigned their 'participant number' in the order of their participation in the study.

Table 1 - Order of study arms, Group 1 and Group 2

Group 1	Group 2		
Practice 1 (simple) RxConnect	Practice 1 (simple) RxConnect		
Practice 2 (complex) RxConnect	Practice 2 (complex) RxConnect		
Test scenario 1 Control	Test scenario 1 RxConnect		
Test scenario 2 Control	Test scenario 2 RxConnect		
Test scenario 3 Control	Test scenario 3 RxConnect		
Test scenario 4 RxConnect	Test scenario 4 Control		
Test scenario 5 RxConnect	Test scenario 5 Control		
Test scenario 6 RxConnect	Test scenario 6 Control		

Figure 1 Example of participants randomised into two groups

Group 1									
1 Participant 5	2 Participant 43	3 Participant 19	4 Participant 3	5 Participant 34	6 Participant 23				
7 Participant 30	8 Participant 27	9 Participant 21	10 Participant 22	11 Participant 7	12 Participant 1				
13 Participant 10	14 Participant 36	15 Participant 32	16 Participant 26	17 Participant 46	18 Participant 14				
19 Participant 33	20 Participant 31	21 Participant 29	22 Participant 15	23 Participant 47	24 Participant 11				
25 Participant 6									
Group 2									
1 Participant 12	2 Participant 28	- Destisinent OF							
		3 Participant 35	4 Participant 41	5 Participant 44	6 Participant 2				
7 Participant 40			4 Participant 4110 Participant 49						
	8 Participant 38	9 Participant 20		11 Participant 16	12 Participant 37				
13 Participant 39	8 Participant 38 14 Participant 18	9 Participant 2015 Participant 25	10 Participant 49	11 Participant 16 17 Participant 17	12 Participant 37 18 Participant 9				

Sample size

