 - How did this compare with your current prescribing practice?
- What effect do you think a system such as RxConnect could have on your prescribing practice?

- o If positive, in what way?
- o If negative, in what way?
- Is there anything that you think would benefit from changing/improving?

Indication-based prescribing workflow questions -

- Did you utilise the option to search by indication as opposed to by medication first?
- How does this align with your current prescribing workflow, both your mental workflow and decision making as well as the physical act of prescribing, for example entering the information onto the prescription?
- Would you consider an indication-*first* prescribing workflow to be better/worse/the same as current prescribing workflows. For example, searching for an indication and then selecting a medication, rather than searching for the medication.

Probes -

- Can you expand on that
- Do you have any examples
 - where this would have been useful...?
 - where this may have hindered...?
 - specific patient groups
 - specific medication types antimicrobial stewardship

10. Appendix 2: Draft Study session standard operating procedure

- 1. Participant will have already received an invitation to participate and agreed a time to take part in the study.
- 2. Participant arrives at pre-specified time, confirms they have received the PIS and has had any questions answered.

- 3. Participant to complete the consent form and an online copy to be sent to the participant to retain for their own records. Participants will be asked to remove or cover any name badges that may identify themselves.
- 4. Audio-visual recording to begin.
- 5. Participant training and briefing-

Participant RxConnect training-

A brief introductory video to be played to the participant showing how to use RxConnect.

Participant study briefing-

Participants to be briefed as to the purpose of the user testing and that scenarios will be presented that may cover a number of conditions, complexities and potentially error prone prescribing tasks, e.g. patients with contraindicated conditions, considerations and less frequently prescribed medications.

- 6. Participant encouraged to 'think aloud' when completing the following tasks. Participants are provided with two prescribing practice scenarios to complete using RxConnect and document the medication order on the paper form provided.

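### Test-block order is randomised, but both groups are trained and practise on RxConnect before any scored scenario, so no control order shows usual practice before exposure

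*Combined protocol and SAP*

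**What the plan says.** Section 3, under the order of the arms, states: "Each participant will be randomly assigned to begin with either the control arm or the intervention arm". Table 1 sets out the two sequences. In both groups the first two rows are "Practice 1 (simple) RxConnect" and "Practice 2 (complex) RxConnect". The first control entry is "Test scenario 1 Control" in Group 1 and "Test scenario 4 Control" in Group 2.

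Appendix 2 gives the same order for every participant. Step 5: "A brief introductory video to be played to the participant showing how to use RxConnect". Step 6: "Participants are provided with two prescribing practice scenarios to complete using RxConnect". Step 7 is a readiness check with a third practice scenario if needed. Only step 8 refers to control-first or intervention-first allocation. Appendix 2 is headed as a draft, but Table 1 in the main text agrees with it.

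Section 3 describes the practice tasks under the intervention arm and continues: "Once familiarised with the software workflow, the test prescribing tasks will be given to the participant". Section 2 makes usual practice the comparator for the primary objective and for the comparative secondary objectives (dose-error magnitude, time, mental load and workflow). The hierarchical task analysis likewise compares RxConnect with participants' usual way of working.

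**The concern.** The control arm is there to show how these prescribers work without the tool. As scheduled, every participant has watched an RxConnect demonstration and worked through at least one simple and one complex RxConnect case, encouraged to think aloud, before the first control scenario. If that exposure changes how people then search, check or calculate on Cerner, the change can reach control data in both sequences. Randomising the order of the blocks cannot balance it out, because there is no unexposed control period in either sequence.

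Workflow is the outcome most open to this, since the interview guide shows that RxConnect offers a search by indication. Time and task load could also move.

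A second asymmetry concerns training. Group 2 goes from practice directly to scored RxConnect tasks. Group 1 has three Cerner scenarios in between, so its RxConnect results alone come after a delay.

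**Working it through.** **Inputs.** Sequences and three control scenarios per participant: Table 1. Video, two practice tasks and an optional third: Appendix 2 steps 5-7. Target of 30-50 participants in equal groups: Section 3.

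**The plan's own figure.** 5 participants per day × 10 days = 50, which reproduces the upper end of the target. No derivation is given for 30, and there is no power calculation to check.

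**RxConnect tasks completed before the first control scenario** (the video is additional):

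| | As written | Training moved to just before the RxConnect block |
|---|---|---|
| Group 1 | 2 practice, or 3 with the optional task | 0 |
| Group 2 | 2 + 3 = 5, or 3 + 3 = 6 | 5 or 6 |

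**Control orders.** 3 × 30 = 90 to 3 × 50 = 150. As written, the fewest RxConnect tasks before control is 2, in Group 1, so the number of unexposed control orders is 0 of 90 to 0 of 150. With training moved, Group 1's control block is unexposed: 3 × 15 = 45 of 90, up to 3 × 25 = 75 of 150.

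**Scored scenarios between training and first RxConnect test task.** As written: Group 1 = 3, Group 2 = 0. With training moved: 0 and 0.

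**Can adjustment recover the baseline?** The analysis section lists group number and scenario number among possible covariates. Group contrasts 2-3 prior RxConnect tasks with 5-6. Neither group has zero, so no model fitted to these data can estimate control performance without exposure unless it extrapolates.

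**What can be compared.** Scenarios 1-3 are always first and 4-6 always second. Group 1's control data are therefore all on scenarios 1-3 and Group 2's all on 4-6. Comparing control results between sequences mixes exposure with scenario set and period, both as written and after the change. Comparing arms within scenarios 1-3 holds scenario and period fixed and is randomised; what it lacks at present is an unexposed control side.

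**Dependence on the scenario count.** Appendix 2 step 8 mentions four scenarios where Table 1 has six in total. The totals above use Table 1; the zero does not depend on that choice.

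**The case against.** The strongest reply is that training everyone up front is a defensible choice. Both groups become used to the simulation ward, cameras, observer and paper scenarios before anything is scored. If training simply moved, Group 1 would begin scored control work cold, which could make control look worse in that group only. This stands, and it is why the fix includes an unscored warm-up on the usual system.

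There are also reasons to expect little carry-over. Participants prescribe at least weekly, the BNF is available in the control arm, RxConnect is not among the control resources, no test scenario is repeated across arms, and patient details are supplied in both. The gap in Group 1 is three scenarios within a session of about 90 minutes, after a readiness check. The general briefing, which would stay first, already warns of error-prone tasks. All of this stands: counts of exposed orders measure exposure, not bias.

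Two stronger readings are tempting and should be resisted. A reader might infer that nobody begins with control, so the randomisation is nominal. Table 1 labels practice separately from test scenarios, and step 8 applies the allocation to the test scenarios; on that basis Group 1 does begin with control. A reader might also infer that the control results are biased, or that Group 1's RxConnect results suffer from forgetting. No document shows either effect or its direction: exposure might help control performance and shrink a difference, or disrupt habits and enlarge one.

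That both groups receive the same training does not settle the matter. It balances groups, but leaves every control observation after exposure.

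**Conclusion.** The point holds as a limit on interpretation. The order of test blocks is randomised, yet 0 of 90-150 control orders measure usual practice before exposure to RxConnect, and the interval from training to RxConnect use is unequal (three scenarios against none). The schedule is certain, being the same in Table 1 and Appendix 2. The consequences are not: the size and direction of any effect cannot be derived from the documents. The counts assume equal groups, Table 1's three control scenarios each, and full completion. Because the study is exploratory and sets no power target, this is a change that should be made because it is cheap, not a flaw that invalidates the study.

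**What to change.** In Table 1 and Appendix 2, place the RxConnect video, practice tasks and readiness check immediately before the RxConnect block in each group.

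- Group 1: general briefing, warm-up on the usual system, control scenarios 1-3, RxConnect training and practice, RxConnect scenarios 4-6.
- Group 2: general briefing, RxConnect training and practice, RxConnect scenarios 1-3, warm-up on the usual system, control scenarios 4-6. Its RxConnect training and test order is unchanged.

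The warm-up is one short unscored scenario in both groups. Scenarios 1-3 then give a randomised comparison of unexposed usual practice with freshly trained RxConnect use, and the training gap is the same in both groups.

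The cost is a redrafted table and procedure plus a few extra minutes per session for the warm-up. What remains is that Group 2's control block still follows exposure, and control results by sequence still differ in scenario set and period. Report both as limitations and do not present that contrast as a carry-over test. If the schedule cannot be changed, describe the randomised factor as the order of test blocks and state that usual practice was measured after RxConnect training.

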A target of 30-50 participants is desirable for this descriptive exploratory mixed methods study. This number has been selected pragmatically to account for approximately 5 participants per day over 10 working days.

Sample size sufficient to calculate statistical significance will not be feasible, therefore a power calculation will not be required.

Data collection and management

Data collection

Data will be collected via audio-visual recording which will take place on the SimWard, Paterson Building, St Marys Hospital. A Scotia Medical Observation Training System (smots, Scotia UK, Edinburgh, UK), with two 3- axis, ceiling- mounted video cameras, and three mobile, high-definition cameras equipped with boom microphones, will be used. The cameras will be angles at the computer screen ann onto the workstation and will not take footage of participants faces. Participants will be asked to remove or cover any name badges that may identify them prior to recording commencing.

The researcher will also keep field notes to assist with later analysis of the observations and interviews. The interviews will be transcribed verbatim by the study researcher prior to thematic analysis.

Participant demographic information will be collected via a short 'demographic questionnaire' at the beginning of the user testing session. Nasa Task Load Index questionnaires will be complete by the participant after each of the intervention arms.

Data management

Physical copies of the consent forms and participant list with pseudonymised participant study numbers will be kept within a locked room with swipe card access to the floor of the department.

Audio-visual recordings of the observations and semi-structured interview (See Appendix 1 for a sample interview guide), psuedoanonymised data capture forms and interview transcripts will be stored on an encrypted hard drive and kept in a locked room with swipe card access to the floor of the department. Interview transcripts will use the participant's psuedoanonymous study code in place of their name.

Publication of study findings will not contain identifiable data, participants will be given a study code name and only referred to by their profession and speciality.

Data and all appropriate documentation will be stored for a minimum of 10 years after the completion of the study.

Duration of study

The duration of the study will be six months from the date of the first participant recruited.

Study outcome measures

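### The unblocked team-generator list does not guarantee the promised equal groups if recruitment ends below 50, so part of any scenario-set or period difference can enter the unadjusted arm comparison

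*Combined protocol and SAP*

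**What the plan says.** Section 3, Order of control vs intervention arm, assigns each participant at random to start with control or with RxConnect and states the intended split: "With an equal number of participants being in each group". The tool is described as "A random team generator", with a pointer to Figure 1. List positions are taken up as people attend: "participants will be assigned their 'participant number' in the order of their participation in the study". No block size, stratification or rebalancing rule is given. Figure 1 is captioned "Figure 1 Example of participants randomised into two groups", and its Group 1 ends at the entry "25 Participant 6".

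Section 3, Sample size, reads "A target of 30-50 participants is desirable for this descriptive exploratory mixed methods study" and explains the number as "approximately 5 participants per day over 10 working days".

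In Table 1, Group 1 does test scenarios 1-3 under control and 4-6 under RxConnect, and Group 2 does the reverse. The scenario order is the same in both groups.

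Under Statistics and data analysis, error counts are compared between arms by a chi-square test, and magnitude of error, time and task load by a Mann-Whitney test. Neither is stated to be adjusted. Group number and scenario number appear only among variables that may be accounted for in a regression sub-analysis, subject to effect size and sample size.

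**The concern.** In this layout, equal group sizes are what make each scenario set appear equally often in each arm. Scenarios 1-3 also always come first, so scenario set and period are the same thing. If one group is larger, one arm receives more of the harder set, or more of the later attempts. A test that pools all control attempts against all RxConnect attempts then counts part of that difference as an effect of RxConnect. The briefing in Appendix 2 tells participants that the scenarios may vary in condition, complexity and proneness to error, and nothing in the documents shows that the two sets are matched.

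Equality is built into the described method only when the whole list is used. The plan allows the study to finish with 20 fewer participants than the example list holds, and gives no rule for keeping the groups level on the way. The outcomes exposed are prescribing errors, time and task load.

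**Working it through.** **The plan's own figure.** 5 participants per day × 10 days = 50. Figure 1 has 25 distinct numbers in Group 1: 1, 3, 5, 6, 7, 10, 11, 14, 15, 19, 21, 22, 23, 26, 27, 29, 30, 31, 32, 33, 34, 36, 43, 46, 47. Group 2 is only partly legible in the extracted text. Its 17 legible numbers do not overlap with Group 1, and I took Group 2 as the complement, which gives 25 + 25 = 50.

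**Step 1: the example list stopped early.** Participant number equals order of attendance, so stopping at N uses numbers 1 to N. Counting the Group 1 numbers up to N:

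| N | Group 1 : Group 2 | (n1 − n2)/N |
|---|---|---|
| 30 | 17 : 13 | 4/30 = 0.133 |
| 35 | 21 : 14 | 7/35 = 0.200 |
| 36 | 22 : 14 | 8/36 = 0.222 |
| 40 | 22 : 18 | 4/40 = 0.100 |
| 45 | 23 : 22 | 1/45 = 0.022 |
| 50 | 25 : 25 | 0 |

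This list is unequal at every stop from 30 to 49. Numbers 29 to 34 all fall in Group 1. A run of six cannot occur with blocks of 2 or 4, where the longest possible run is four, so the example was not blocked in that way.

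**Step 2: a fresh list of the same kind.** For a random 25/25 split of 50 stopped at N, the Group 1 count a has probability C(25, a) × C(25, N − a) / C(50, N).

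- N = 30: exact balance 0.227; difference of 4 or more 0.387; of 6 or more 0.148; mean absolute difference 2.7; SD of the difference 3.5.
- N = 40: exact balance 0.275 (27% before the third decimal is rounded); difference of 4 or more 0.289.
- At odd N, exact equality is impossible under any method.

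**Step 3: what imbalance does to the arm comparison.** Let p1 be the error rate in scenarios 1-3, p2 the rate in scenarios 4-6, and suppose RxConnect has no effect. Then

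- control rate = (n1·p1 + n2·p2)/N
- RxConnect rate = (n1·p2 + n2·p1)/N
- RxConnect − control = [(n1 − n2)/N] × D, with D = p2 − p1.

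D includes any period effect. Check at 17:13 with p1 = 20% and p2 = 40%: control = (17 × 0.2 + 13 × 0.4)/30 = 28.7%; RxConnect = (17 × 0.4 + 13 × 0.2)/30 = 31.3%; difference 2.7 points.

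The documents give no error rates, so D is an assumption, shown over a range (leak in percentage points):

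| Split | D = 10 | D = 20 | D = 30 |
|---|---|---|---|
| 17:13 (N = 30) | 1.3 | 2.7 | 4.0 |
| 21:14 (N = 35) | 2.0 | 4.0 | 6.0 |
| 22:14 (N = 36) | 2.2 | 4.4 | 6.7 |
| 22:18 (N = 40) | 1.0 | 2.0 | 3.0 |
| 23:22 (N = 45) | 0.2 | 0.4 | 0.7 |

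**Step 4: scale.** At an assumed error rate of 30%, three scenarios per arm and clustering ignored, the standard error of the arm difference is √(2 × 0.3 × 0.7/(3N)): 6.8 points at N = 30 and 6.2 at N = 36. Over random lists at N = 30 with D = 20, the leak has mean zero and root mean square 3.5/30 × 20 = 2.3 points. That raises the standard error from 6.8 to √(6.8² + 2.3²) ≈ 7.2.

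The session procedure in Appendix 2 mentions 4 scenarios where Table 1 has 3 per arm. The two should be reconciled, but the fraction (n1 − n2)/N does not depend on that number.

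**The case against.** Four points can be made for the plan.

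1. **Figure 1 is only an example.** A reader might infer that the trial will run on the printed list, or that its real list is certainly one draw of 50. The documents do not say so; smaller batches are not described, but they are not excluded. The splits in Step 1 illustrate the method and do not forecast this trial. What stands is that the text cites Figure 1 for the method and mentions nothing that would hold the groups level.
2. **Inequality is not certain.** A reader might infer that equal groups fail wherever recruitment stops between 30 and 49. That is true of the printed list, but a fresh list can balance by chance at any even number. The supportable statement is that equality is not guaranteed.
3. **The leak is small and has no preferred direction.** It averages zero over possible lists, vanishes if the two sets and periods are equally difficult, and is usually a fraction of a standard error. The control-arm description suggests some intent to make the tasks comparable, and the study calls itself descriptive and exploratory. All this stands and limits the weight of the point. It does not remove it, because the study will use one realised list. With a large D and a marked imbalance the leak can reach about one standard error (6.7 against 6.2 points at 22:14 with D = 30).
4. **Adjustment is foreseen.** Scenario and group number are listed as possible covariates, and adjusting for scenario would deal with the leak directly, including imbalance caused by withdrawals. But the adjustment is optional, conditional and confined to a sub-analysis, so the main comparison is unprotected.

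**Conclusion.** The point holds in a limited form. The promise of equal groups is not secured by the described method at any total below 50, and the plan allows totals from 30. Because scenario set and period are tied to arm within each group and the main tests are unadjusted, a fraction (n1 − n2)/N of any scenario-set or period difference passes into the arm comparison. For error rates this is 1.3 to 4.0 points at 17:13 for assumed differences of 10 to 30 points.

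The same route is open for time and task load. The identity applies to mean differences there too, but the documents give nothing from which to size it, and it does not translate directly to the Mann-Whitney statistic.

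The result rests on three assumptions: that the operative list is built as Figure 1 suggests, that D is not zero, and, for the comparison with the standard error, a 30% error rate with clustering ignored. It does not support a claim that the comparison is systematically biased towards either arm or that the design is unsound. It is a modest, avoidable source of error.

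**What to change.** In Section 3, replace the team draw with a computer-generated allocation list in permuted blocks of randomly varying size 2 and 4, issued in order of attendance. Allocated group sizes then differ by at most 2 whenever recruitment stops. At N = 30 the largest possible leak becomes 2/30 × D, which is 0.7, 1.3 or 2.0 points for D of 10, 20 or 30, against 1.3, 2.7 and 4.0 on the example list.

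The cost is one sentence in the protocol and a new list. Allocation becomes slightly more predictable, which matters little because every participant receives both arms. Blocking balances those allocated, not necessarily those analysed after withdrawals. Making the scenario adjustment a committed part of the main analysis would cover that remainder, but the blocked list is worth having whichever analysis is used.

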4. PARTICIPANT RECRUITMENT

A convenience sample of study participants will be recruited from across Imperial College NHS Healthcare Trust. Study participants will be doctors and non-medical prescribers whose usual course of work involves the prescribing of medication.

Targeted sampling may be conducted to gain participants from a wide range of specialities/ levels of seniority including but not limited to-

- Seniority-
 - Foundation Year 1 and 2, Senior House Officers, Registrars, Consultants, Non-medical prescribers (nurses and pharmacists)
 - Specialities,
 - Medical, Surgical, Paediatrics, Neonatal, Emergency medicine

Department leads and managers will be approached to gain permission prior to any approach of relevant medical staff and will be asked to disseminate invitations to participate in this study. Staff will be sent an email via their trust email address via the departments 'email group'. In addition, an advert will be placed on the trust intranet and further advertisement of the study through word of mouth via established working relationships within ICHT and ICL.

Participants will be provided with a participant information sheet at least a week prior to commencing any recruitment/data collection.

On the day of participating, participants will have the option to ask any further questions before deciding to take part and a copy of the participant information sheet will be available as either paper copy or via email as a PDF.

As participants will be NHS staff, there will be an expectation that participants will have adequate English language skills (reading, written and verbal) to be able to provide informed consent and participate. However, if adaptations are required for a member of staff to participate, (such as information sheets printed in larger font/different colours) this will be accommodated as per any normal adaptations required for working.

Participation in the study should take approximately 90 minutes and will not detract from clinical duties, where possible participation should be during non-clinical hours and/or when appropriate clinical cover is available.

Inclusion Criteria

- Willingness to consent and participate
- Medical doctor Foundation year 1 and above OR registered non-medical prescriber (e.g. nurses or pharmacists)
- Regular (at least weekly) experience in prescribing medications as part of working role

Exclusion Criteria

- Infrequent prescribing practice (less than once a week)
- Not willing to participate

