- 7. Confirm that the user is happy with how to use RxConnect and have any questions answered, a third prescribing practice scenario can be used if required.
- 8. Depending on allocation of control first or intervention first the participant is to complete 4 prescribing scenarios independently, they may 'think aloud' if the desire but this should not distract from the task.
- 9. Following each individual scenario, the participant is to complete a NASA TLX form.
- 10. Qualitative interview-Confirm that the participant consents to continue with a short semi-structured interview. Conduct the interview using the topic guide
- 11. Discontinue audio-visual recording.

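### Order groups come from an unconcealed list keyed to attendance order, so the next attendee's group can be known at booking and when extra RxConnect practice is decided

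*Combined protocol and SAP*

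**What the plan says.** Section 3 (Order of control vs intervention arm) randomises each participant to start with control (Group 1) or RxConnect (Group 2): "With an equal number of participants being in each group". The tool is "A random team generator" on a public website. Figure 1, captioned "Example of participants randomised into two groups", shows participant numbers already divided between the groups. The link from person to list is that "participants will be assigned their 'participant number' in the order of their participation in the study". In Table 1, Group 1 does scenarios 1-3 with control and 4-6 with RxConnect, and Group 2 does the reverse.

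Appendix 2 gives the sequence. Step 1: "Participant will have already received an invitation to participate and agreed a time to take part in the study". Consent is step 3, training step 5 and the two RxConnect practice tasks step 6. Step 7 adds that "a third prescribing practice scenario can be used if required", with no criterion beyond confirming that the participant is comfortable with the system. The allocation is first used in step 8. Section 4 describes a convenience sample and adds: "Targeted sampling may be conducted to gain participants from a wide range of specialities/ levels of seniority".

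The document names no holder of the list, no envelopes and no time at which the group is revealed. The locked storage under Data management covers consent forms, the participant list and study data. It protects confidentiality and does not hide the allocation from the study team.

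**The concern.** Once such a list exists, the group of the n-th attendee is a lookup. Two discretionary decisions fall before the allocation is used: who is booked into which session, and who receives a third RxConnect practice task. A member of the research team is present throughout the session, and nothing says that this person is unaware of the group.

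The first decision matters because Table 1 puts the two scenario sets in opposite arms in the two groups. If prescribers whose speciality suits one set are concentrated in one group, their advantage falls more on one arm than on the other. The second matters because extra practice affects only RxConnect results. If its use depends on order, the two groups no longer differ only in order and scenario assignment. Errors, time and task load are all exposed. Neither problem can be repaired once sessions have run.

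**Working it through.** **The plan's own figure.** The target is 30-50 participants. The upper end is session capacity: 5 per day x 10 working days = 50, or 25 per group. This reproduces. Figure 1 lists 25 distinct numbers for Group 1, consistent with a complete list of 50 split in half.

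**How predictable is the next group?**
- List visible: the next attendee's group is certain. Later groups are known only if bookings are kept in order, because a no-show shifts every later number.
- List hidden, but a fixed 25:25 split and past groups known: the best guess is right on average [25 + (2^50/C(50,25) - 1)/2] = 28.95 times in 50, or 57.9%. A simulation of 20,000 lists gave 28.94. Pure chance is 50%.

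**General ability.** Let Group 1 exceed Group 2 by d on every scenario. The RxConnect-minus-control contrast shifts by -d on scenarios 1-3 and by +d on scenarios 4-6. Pooled: 0.5 x (-d + d) = 0. It cancels under an additive model when everyone completes both arms.

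**Speciality suited to one scenario set.** With equal groups:
- RxConnect mean = 0.5 x (Group 1 on 4-6 + Group 2 on 1-3)
- Control mean = 0.5 x (Group 1 on 1-3 + Group 2 on 4-6)

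Let a speciality have an advantage a on scenarios 1-3 relative to 4-6, with shares p1 and p2 in the two groups. The arm difference then shifts by 0.5 x a x (p2 - p1), which does not cancel. The documents give neither a nor the shares, so the inputs below are assumptions. They use a speciality with a 20% share, that is 10 of 50 people, so the share difference cannot exceed 10/25 = 0.4. A difference of 0.2 lies between a 7:3 split (0.16) and an 8:2 split (0.24).

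| Share difference | Advantage 20 points | Advantage 30 points |
|---|---|---|
| 0.2 | 0.5 x 0.2 x 20 = 2 points | 0.5 x 0.2 x 30 = 3 points |
| 0.4 (all ten in one group) | 0.5 x 0.4 x 20 = 4 points | 0.5 x 0.4 x 30 = 6 points |

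For comparison, the chance SD of the share difference is sqrt(2 x 0.2 x 0.8/25) = 0.113. That corresponds to 0.5 x 0.113 x 20 = 1.1 points, or 0.5 x 0.113 x 30 = 1.7 points.

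**Third practice task.** Let it improve RxConnect results by g, and let shares u1 and u2 of the two groups receive it. The contrast moves by u2 x g on scenarios 1-3 and by u1 x g on scenarios 4-6. With equal groups the pooled contrast moves by 0.5 x (u1 + u2) x g, which is the overall share times g. Shares of 50% and 50%, 75% and 25%, or 100% and 0% all give 0.5 x g. Knowing the group allows u1 and u2 to be set apart, which distorts the per-scenario and order comparisons. The pooled movement depends on the overall share, which concealment does not control.

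**The case against.** The strongest reply is that this is a small exploratory study with no power calculation, in which each participant is used in both arms and Table 1 counterbalances every scenario. The documents do not describe scenario content, so nothing shows that the two sets favour different specialities. Attendance depends on non-clinical time or clinical cover, which limits steering, and targeted sampling is meant to widen the range of participants, with no link to particular slots. The Statistics section also lists group, scenario, complexity, grade and speciality as possible adjustment variables.

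Most of this stands, and it is why the effect is likely to be small. The adjustment is a weak safeguard: it is conditional on effect and sample size, and a speciality main effect would not remove an interaction between speciality and scenario set. The chi-square and Mann-Whitney tests are unadjusted.

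A reader might go further and infer four things that the documents do not support:
- That every future slot is known with certainty. Numbers follow attendance, so certainty covers only the next person. Figure 1 is an example, so its last numbers say nothing about the real list.
- That the bias from extra practice is proportional to the difference in its use between groups. The pooled RxConnect mean follows the overall share.
- That randomised order is the sole safeguard. Counterbalancing and within-participant comparison also protect.
- That tailoring will occur. The text shows only that it is possible.

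That the list is drawn beforehand is itself an inference, since no date is given. It is a strong one: the tool needs the full list to form equal groups, and sequential numbers can be looked up only on a list that already exists.

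**Conclusion.** The concern holds in limited form. As written, the plan leaves the next attendee's group open to those who book and run sessions, during two decisions that should be made without it. General ability cancels in the pooled comparison. The remaining risks are a speciality-by-scenario-set imbalance and third-task use that differs by order. On assumed inputs the first is worth 2 to 6 points on the error rate; its true size cannot be obtained from the documents, and the upper figure requires every member of a speciality to be placed in one group. The likely effect is small. The change is still worth making, because the primary objective is an arm comparison of errors, the cost is slight, and concealment cannot be added afterwards.

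**What to change.** 1. In Section 3, state that the list, or a set of sequentially numbered opaque sealed envelopes, is held by an existing team member who neither books nor runs sessions.
2. In Appendix 2, insert a line between steps 7 and 8 revealing the group only then, after consent, training and the third-task decision.
3. In step 7, state a fixed criterion for the third practice task that applies equally to both groups. Concealment alone does not stop extra practice from favouring RxConnect overall.
4. Record whether the third task was used and report its use by group.

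The cost is a few sentences and, if chosen, the envelopes; no extra participants are needed. No added staff are needed if a suitable team member exists, which the documents do not confirm. Both workstations must be ready before each session. With a fixed 25:25 list, the next group could still be guessed about 58% of the time by someone who tracks past groups, which is a modest residue compared with an open list.
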